#### 6.6.1 LSFU Week 4, 8, 24, and 36 Visit

LSFU Week 4, 8, 24, and 36 study visits have the following target dates as calculated from the last administration of injectable study product (or confirmatory positive pregnancy test result):

- LSFU Week 4 target date is 28 days after last injection/positive pregnancy test
- LSFU Week 8 target date is 56 days after last injection/positive pregnancy test
- LSFU Week 24 target date is 168 days after last injection/positive pregnancy test
- LSFU Week 36 target date is 252 days after last injection/positive pregnancy test

These visits each have a target window of -14 days/+28 days from the target visit date.

^ For participants of childbearing potential.

LSFU Week 4, 8, 24, and 36 Visit Procedures		
Behavioral and		• Provide contraceptive counseling, if indicated^
Counseling		Provide adherence counseling
Clinical		Update medical and medications history
		Perform targeted physical exam
		Identify/review/update adverse events
Laboratory	Blood	Collect blood for:
		• Hematology: CBC (WBC, RBC, hemoglobin, hematocrit, MCV, MCHC) with differential, ANC (absolute neutrophil count), and platelet count
		• Chemistries: Creatinine, eGFR, CK, Direct bilirubin, Total bilirubin, BUN, AST, ALT, Lipase, Albumin
		• HIV-1 RNA
		PK evaluation: Single sample
	Blood or Urine	Pregnancy test^

^ For participants of childbearing potential.

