## 6.6.2 LSFU Week 48 /Early Termination Visit

The LSFU Week 48 Visit is targeted to take place 336 days after the last administration of injectable study product (or confirmatory positive pregnancy test result), with a target window of  $\pm 42$  days from the target visit date. These same visit procedures will be conducted as an Early Termination visit for participants withdrawing or terminating from the study prior to scheduled completion of study follow-up, instead of their regularly scheduled study visit, for a final series of evaluations. All participants completing this visit, whether as the LSFU Week 48 Visit (per the LSFU visit schedule) or as an Early Termination visit, will exit the study.

Scheduling and completion of Early Termination visits will be in consideration of participant withdrawal or termination; visit procedures may be combined with an ongoing study visit. Any procedures conducted within 14 days of an Early Termination visit need not be repeated, with the following target dates for completing the Early Termination visit:

- For Cohort 1 and Cohort 2a Step 1 participants not progressing to the injection phase, an Early Termination visit is targeted to be completed 28 days after the participant's last oral study product use; the Early Termination visit may be completed sooner, if necessary. For these participants, a PK evaluation will not be performed at this visit.
- For any participant being followed per the LSFU visit schedule and withdrawing from the study, an Early Termination visit is targeted to be completed within 28 days (inclusive) of the previous study visit.

Participants completing an Early Termination visit will be followed until resolution (return to baseline) or stabilization of any adverse events per Section 8.1.

Refer to Section 6.8 for the definition of scheduled completion of follow-up, and additional considerations for participants exiting the study (whether scheduled completion of follow-up or an early termination visit). Refer to Section 8.5 for criteria for participant withdrawal or premature termination from the study. The IMPAACT 2036 MOP provides further guidance on Early Termination visit scheduling considerations.

LSEU Week	48 /Farly	Termination Visit Procedures	

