#### 10.2.4 Other Outcome Measures

- CAB and RPV concentrations 8 to 48 weeks following final IM dose
- PO dosing: Wk. 2 AUC, CL/F, Cmax, Tmax, and pre-dose concentrations (C0) by administration mode

Table 11.
Pharmacology Estimands

	Primary PK Estimand (Cohort 1)
A primary question of interest	What is the PK profile of repeat-dose pharmacokinetics CAB+RPV (~4 weeks of oral lead-in followed by ~20 weeks of injectable) (orally lead-in followed by injectable through Week 24) in virologically suppressed children living with HIV-1, two to less than 12 years of age?
Attributes	
Population	Virologically suppressed children living with HIV, 2 to less than 12 years of age, who received CAB + RPV through Week 24.
Endpoints/ Variables	
 
o PO: Wk. 2 AUC, CL/F, Cmax, Tmax, and pre-dose concentrations (C0)
 
o LA: C5WK, C12WK, and Ct prior to IM doses through Wk. 24 and accumulation ratio (Wk. 24:Wk. 8).
 

	As shown in Table 10
Treatment condition	Oral CAB + Oral RPV once daily through Week 4, followed by LA CAB + LA RPV Q4W or Q8W through Week 24 (see Schema on treatment details).

Intercurrent events (ICE)	
 
o Premature permanent discontinuation of study drugs for any reasons (e.g., death) during treatment phase through Week 24 has impact on PK assessment. While-on-treatment strategy will be applied to address this ICE.
 
o Use of prohibited medications that potentially has significant impact on PK concentrations per clinical pharmacologist will also be addressed by 'while-on-treatment strategy'.
 

Population- level summary	Summary statistics e.g., arithmetic mean, geometric mean, median, standard deviation, minimum, maximum, and coefficient of variation, 90% confidence interval, etc.

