  - Wk. 2: Day 12 16 post-dose,
  - o Pre-dose prior to injections at Wk. 4, Wk. 12, Wk. 20, Wk. 28, Wk. 36, Wk. 44.

All Cohorts (Cohorts 1, 2a and 2b)

- LSFU
  - o Single PK sample collected at LSFU Week 4, 8, 24, 36 and 48 visits.

Assay Site: Plasma pharmacokinetic samples collected will be sent to the IMPAACT Pharmacology Laboratory listed in the IMPAACT 2036 LPC for both CAB and RPV containing specimens. Sample collection, processing, storage and shipping details are provided in the IMPAACT 2036 LPC.

Methods to be used: All assay methods will be standardized with a filed Methods Report, under Good Laboratory Practice (GLP) conditions and cross-validated with primary assay providers used for CAB and RPV. The assays will be performed using high-performance liquid chromatography and tandem mass spectrometry (HPLC/MS/MS).

Reporting of Assay Data: PK samples from participants in Cohort 1 who are following the Rich Sampling Schedule will have assays performed in real-time through Week 24. Assaying of samples from the Wk. 32 through the Wk. 48 and Wk. 72 visits in the Rich Sampling Schedule, and all assays from the Limited Sampling Schedule (Cohorts 1 and 2a) may be performed in batches (refer to LPC for shipping schedule), and upon team request. PK samples from participants in Cohort 2b who are following the IM-only Sampling Schedule will have the assays performed in real-time up through Week 20. Samples from Wk. 28 through Wk. 44 may be assayed in batches and upon team request. PK samples collected from any Confirmation of Virologic Failure visit will be assayed as requested by the team.

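### The LSFU Week 4 and Week 8 visit windows overlap on Days 42 to 56, so two of the five washout time points can be taken almost together

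*Protocol*

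**What the plan says.** Section 6.6.1 of the Protocol fixes the early LSFU targets: "LSFU Week 4 target date is 28 days after last injection/positive pregnancy test" and "LSFU Week 8 target date is 56 days after last injection/positive pregnancy test". The next two targets are Days 168 and 252. One tolerance covers all four visits: "These visits each have a target window of -14 days/+28 days from the target visit date". Section 6.6.2 puts the last visit at Day 336, with 42 days either side.

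Section 10.3 gives the sampling plan: "Single PK sample collected at LSFU Week 4, 8, 24, 36 and 48 visits". HIV-1 RNA, haematology and chemistry are drawn at the same visits. Section 10.2.4 defines the washout outcome as "CAB and RPV concentrations 8 to 48 weeks following final IM dose".

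Section 6.1.1 says that Appendix II summarises target dates and windows for every visit type, but Appendix II has no LSFU rows. Section 6.6.1 is therefore the only place where the Week 4 and Week 8 windows are set.

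**The concern.** A tolerance of 14 days before and 28 days after spans 42 days, but the Week 4 and Week 8 targets are only 28 days apart. The two windows must overlap. Both visits share one procedures table, so an attendance in the overlap can be recorded as either, and two compliant visits can be a few days apart.

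Each child in LSFU contributes five scheduled washout samples. If two are nearly simultaneous, one adds little, and the same holds for the viral load and safety tests drawn with it. The visit label and the outcome definition can also disagree, because a compliant Week 8 sample may be taken before 8 weeks have passed.

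**Working it through.** **Inputs.** Targets of Day 28, 56, 168 and 252, with -14/+28 days (Section 6.6.1); Day 336 with 42 days either side (Section 6.6.2). The targets reproduce as week x 7: 4 x 7 = 28, 8 x 7 = 56, 24 x 7 = 168, 36 x 7 = 252, 48 x 7 = 336. The Protocol gives no overlap figure to reproduce.

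**Windows** (target minus lower tolerance, to target plus upper tolerance):

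| LSFU visit | First day | Last day |
|---|---|---|
| Week 4 | 28 - 14 = 14 | 28 + 28 = 56 |
| Week 8 | 56 - 14 = 42 | 56 + 28 = 84 |
| Week 24 | 168 - 14 = 154 | 168 + 28 = 196 |
| Week 36 | 252 - 14 = 238 | 252 + 28 = 280 |
| Week 48 | 336 - 42 = 294 | 336 + 42 = 378 |

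**Overlap of Weeks 4 and 8.** From the later opening day (42) to the earlier closing day (56), inclusive: 56 - 42 + 1 = 15 days.

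**Other adjacent pairs.** Week 8 closes on Day 84 and Week 24 opens on Day 154. Week 24 closes on Day 196 and Week 36 opens on Day 238. Week 36 closes on Day 280 and Week 48 opens on Day 294. None overlaps, so the problem is confined to Weeks 4 and 8.

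**Week 8 against Section 10.2.4.** The window holds 84 - 42 + 1 = 43 days. Those before 8 weeks (Day 56) are Days 42 to 55: 55 - 42 + 1 = 14 days, and 14/43 = 33% of the permitted days. This counts days; it is not the probability of an early visit.

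**A comparison within the Protocol.** In Appendix II, Week 2 closes on Day 14 + 6 = 20 and Week 4a opens on Day 28 - 7 = 21. There the windows meet without overlapping.

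**Check of possible changes.**

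- Week 4 at -14/+13 closes on Day 28 + 13 = 41. With Week 8 opening on Day 42 the overlap is 0 days, but samples on Days 41 and 42 would still be allowed, so abutting windows alone are not enough.
- With a 14-day minimum interval added, a Week 4 visit on Day 41 puts Week 8 at Day 55 or later, leaving 84 - 55 + 1 = 30 permitted days.
- If Week 8 opens on Day 56 instead, the closest possible pair is 56 - 41 = 15 days apart, and no Week 8 sample falls before 8 weeks.
- Opening Week 8 on Day 56 without touching Week 4 leaves a one-day overlap, on Day 56.

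**The case against.** The best defence is that the windows are tolerances, not plans. Section 6.1.1 tells sites to aim for the target date, to use the window only when necessary, and to make up missed PK and safety evaluations at an interim or the next visit. A child seen late for Week 4 can still attend Week 8 up to Day 84. Washout PK is an Other objective, it concerns only children who enter LSFU, and no dose decision depends on it. All this stands and limits the weight of the point, but it does not separate the windows.

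Several stronger readings are tempting, and the documents do not support them.

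- **The Week 8 value fails its outcome.** It need not: Days 56 to 84, which are 29 of the 43 permitted days, satisfy Section 10.2.4. The range can also be read as the nominal Week 8 to Week 48 visits, which Section 6.6 schedules only approximately. On that reading the mismatch is one of wording.
- **The overlap produces a large spread in concentrations.** Any spread across the Week 8 window comes from its 42-day span, which Weeks 24 and 36 share. With the 200-day RPV half-life in Section 1.2.2 the ratio across that span is 2^(-42/200) = 0.87. The Protocol gives no CAB half-life from which to derive a comparable figure.
- **Sampling times will be ignored in the analysis.** Section 6.16.1 requires the date and time of each PK collection to be recorded, and Section 10.5 lists them among the analysis inputs. Further detail is left to the PK SAP.
- **An early-decline estimate is lost.** None is planned. Section 10.5.2 foresees only a terminal half-life, if the data permit.
- **The first viral load after stopping is generally delayed.** Week 4 may be as late as Day 56, but children on Q8W dosing already have laboratory tests only at injection visits (Section 6.1.2), which Appendix II allows to be up to 63 days apart. The point has some force only for Q4W dosing.

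**Conclusion.** The point holds as a minor, specific defect in the visit windows. LSFU Weeks 4 and 8 share 15 permitted days, are the only LSFU pair that overlaps, and have no stated minimum interval. One of five washout PK, HIV-1 RNA and safety time points can therefore be wasted while every visit remains compliant. Recorded sampling times allow an honest analysis of the samples taken, but cannot supply one that was never taken at a distinct time. The possible early Week 8 sample (14 of 43 permitted days) is a secondary inconsistency.

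This is a statement about what is permitted, not a forecast of how often it will happen. It assumes that the study-specific Manual of Procedures, which is not at hand, adds no spacing rule; Section 6.1.1 refers to it for scheduling guidance in general. Days are counted from the last injection. After a discontinuation for pregnancy the LSFU visits count from the positive test instead; the overlap is the same, but the comparison with Section 10.2.4 then depends on the time from injection to test.

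**What to change.** 1. In Section 6.6.1, give LSFU Week 4 its own window, for example -14/+13 days (Day 14 to 41), with Week 8 opening on Day 42.
2. State a minimum interval between the two visits, for example 14 days.
3. Add the LSFU rows, including that interval, to Appendix II, so that it covers all visit types as Section 6.1.1 says.
4. Align Section 10.2.4: either word the outcome as concentrations at the nominal LSFU Week 8 to Week 48 visits, or open the Week 8 window on Day 56. The second option secures at least 15 days between the visits without a separate interval rule, but excludes any early Week 8 attendance.

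The cost is a wording change and a few more out-of-window Week 4 visits, because that window shrinks from 43 days to 41 - 14 + 1 = 28 days. Weeks 24, 36 and 48 need no change for this reason.

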## 6.6.2 LSFU Week 48 /Early Termination Visit

The LSFU Week 48 Visit is targeted to take place 336 days after the last administration of injectable study product (or confirmatory positive pregnancy test result), with a target window of  $\pm 42$  days from the target visit date. These same visit procedures will be conducted as an Early Termination visit for participants withdrawing or terminating from the study prior to scheduled completion of study follow-up, instead of their regularly scheduled study visit, for a final series of evaluations. All participants completing this visit, whether as the LSFU Week 48 Visit (per the LSFU visit schedule) or as an Early Termination visit, will exit the study.

Scheduling and completion of Early Termination visits will be in consideration of participant withdrawal or termination; visit procedures may be combined with an ongoing study visit. Any procedures conducted within 14 days of an Early Termination visit need not be repeated, with the following target dates for completing the Early Termination visit:

- For Cohort 1 and Cohort 2a Step 1 participants not progressing to the injection phase, an Early Termination visit is targeted to be completed 28 days after the participant's last oral study product use; the Early Termination visit may be completed sooner, if necessary. For these participants, a PK evaluation will not be performed at this visit.
- For any participant being followed per the LSFU visit schedule and withdrawing from the study, an Early Termination visit is targeted to be completed within 28 days (inclusive) of the previous study visit.

Participants completing an Early Termination visit will be followed until resolution (return to baseline) or stabilization of any adverse events per Section 8.1.

Refer to Section 6.8 for the definition of scheduled completion of follow-up, and additional considerations for participants exiting the study (whether scheduled completion of follow-up or an early termination visit). Refer to Section 8.5 for criteria for participant withdrawal or premature termination from the study. The IMPAACT 2036 MOP provides further guidance on Early Termination visit scheduling considerations.

LSEU Week	48 /Farly	Termination Visit Procedures	
Behavioral and Counseling		
 
Provide contraceptive counseling, if indicated^
 
Administer participant acceptability/tolerability assessment based upon participant age, as specified in the IMPAACT 2036 MOP (only for early termination visit)
 
Parent/caregiver acceptability/tolerability assessment (only for early termination visit)
 
	
Clinical		
 
Update medical and medications history
 
Perform complete physical exam
 
Identify/review/update adverse events
 
Perform additional evaluations per Section 8.3 and/or if clinically indicated (consult CMC if indicated)
 
	
Laboratory	Blood	
 
Collect blood for:
 
Hematology: CBC (WBC, RBC, hemoglobin, hematocrit, MCV, MCHC) with differential, ANC (absolute neutrophil count), and platelet count
 
Chemistries: Creatinine, eGFR, CK, Direct bilirubin, Total bilirubin, BUN, AST, ALT, Lipase, Albumin
 
HIV-1 RNA
 
Stored whole blood for genotypic resistance testing and HIV-1 subtyping (only for Early Termination visit)
 
PK evaluation: Single sample (except not at the Early Termination visit for Step 1)
 
	
Blood or Urine		Pregnancy test^	

^ For participants of childbearing potential.

# 6.7 Confirmation of Virologic Failure Visit

Any participant with a plasma HIV-1 RNA level ≥200 copies/mL after enrollment should be recalled to the clinic for completion of the Confirmation of Virologic Failure visit for confirmatory testing 2-4 weeks after specimen collection for the initial test. Scheduling of this visit within the timeframe specified should also be in consideration of potential causes for virologic failure such as intercurrent illness, recent immunizations, inadequate adherence, interruptions of study product, or other extenuating circumstances. For participants receiving injectable study product, confirmatory test results should ideally be obtained and reviewed prior to the next scheduled administration of injectable study product. While injection study visits for these participants may be delayed within the respective target visit window, injectable study product must not be withheld for pending confirmatory testing or results.

Confirmation of Virologic Failure visit procedures may be combined with regularly scheduled visit procedures if they are performed within the target window of a regularly scheduled visit. In addition to the protocol-specific procedures listed in this section, study staff may complete other tasks and assessments consistent with local standards of care and site SOPs.

The viral load results from the Confirmation of Virologic Failure visit will determine whether the participant has met the criteria of virologic failure for the study (See Section 8.3 for the definition and management of virologic failure). Viral load results should be provided to participants and may be used to guide adherence counseling. See Section 6.14 for additional details on adherence counseling.

Confirmation	on of Virolo	ogic Failure Visit Procedures	
Behavioral and		Provide contraceptive counseling*^	
Counseling		Provide adherence counseling*	
Clinical		Obtain interval medical and medications history	
		Perform targeted physical exam	
		Identify/review/update adverse events	
		Perform additional evaluations per Section 8.3 and/or if clinically indicated	
		(consult CMC if indicated)	
Laboratory	y Blood Collect blood for:		
		• HIV-1 RNA	
		Plasma for genotypic and phenotypic resistance testing	
		PK evaluation: Single sample	
Blood or		Pregnancy test^	
Urine			

\*If indicated

# 6.8 Study Exit

Participants may exit the study at different timepoints, with the following considered as scheduled study completion of follow-up:

- Cohort 1 participants completing all follow-up visits per protocol, through Week 72; Cohort 2a participants completing all follow-up visits per protocol, through Week 48; Cohort 2b participants completing all follow-up visits per protocol, through Week 44
- Participants completing all follow-up visits through LSFU Week 48, for participants in the LSFU visit schedule (see Section 6.6 above)

Any participant withdrawing or terminating from the study prior to these timepoints is considered as prematurely terminating from the study and the LSFU Week 48 study visit will be conducted as an Early Termination visit, instead of their regularly scheduled study visit, for a final series of evaluations. All visit procedures as described in and applicable to Section 6.6.2 will be completed for an Early Termination visit, with additional procedures and exceptions as noted.

At any study exit visit (scheduled completion of follow-up or an early termination visit), arrangements should be made to provide all clinically meaningful results to the participant and the participant's parent or guardian. Study staff should provide the participant and parent or guardian with information on how to remain in contact with study staff (if desired) and how to learn about the results of the study when available. Study staff should also provide information, counseling, and referrals to non-study sources of care and treatment for the participant, as applicable. See Section 8.1 regarding management of adverse events at study exit, and Section 8.6 for additional considerations regarding participant withdrawal or termination.

Planning for transition to non-study care and treatment for participants exiting the study should begin prior to the participant's scheduled study exit visit, and the transition should be implemented at the participant's scheduled study exit visit. Study staff will complete a final study contact, with the participant and the participant's parent or guardian, if applicable, within 4 weeks of the participant's study exit visit to confirm the transition and should be documented in each participant's study chart. These contacts are not expected to be entered into eCRFs.

^ For participants of childbearing potential.

# 6.8.1 Reasons to Postpone Study Exit

In the following circumstances, a participant's planned study exit may need to be postponed to allow for additional participant management and eCRF data collection:

- If a participant becomes pregnant while on study: Refer to Section 8.2 for comprehensive guidance on pregnancy management
- If, based upon results from the LSFU Week 48 visit, a Confirmation of Virologic Failure visit is indicated: A Confirmation of Virologic Failure visit should be conducted (refer to Section 6.7).
- If the participant has any Grade 3 or higher adverse event at their last scheduled study visit: Refer to Section 8.1.

Participants who meet the above criteria will exit the study upon completion of the last required data collection point.

# 6.9 Procedures for Oral Study Product Dispensing and Continued Injectable Study Product Administration

The following procedures must be performed on the same day as and prior to dispensing oral study product or administering a study product injection, to assess for any indication of study product hold or permanent discontinuation:

- Clinical evaluations per the respective scheduled study visit (including participant weight to confirm the appropriate weight-band injectable dosing regimen)
- Laboratory test results from the previous study visit obtained and reviewed for indication of study product hold or permanent discontinuation (see Section 8.4-8.5)
- For participants of childbearing potential, a negative pregnancy test result. For participants of childbearing potential, assessment of contraceptive requirements and use (See Section 6.13)

See Section 8 for details regarding participant management, including additional details related to deferring study product due to managing adverse events and other indications.

